## 2.6 Timing of Analysis

A data lock will be used for the primary analysis. The data lock will occur upon the completion of ERC adjudication on the study data and completion of related data quality assurance. An ERC Charter will define the scope of ERC review as well as the timeline for the data adjudication. The data lock will include the mature data on the primary and key secondary endpoints for the study participants. If the first lock occurs prior to the completion of 1 year of follow-up on all study participants, a second data lock will be performed in order to permit analysis of secondary endpoints requiring extended follow-up.

## 2.7 Software

All analyses will be conducted using SAS 9.4 or higher software and R version 3.1.0 or higher.

## 2.8 Analysis Populations

### 2.8.1 Primary Analysis Population

Participants will be analyzed according to the intent to treat (ITT) principle for this study, i.e. according to the treatment groups to which they were randomized, regardless of whether the assigned treatment was administered. Any participant who receives a treatment randomization number will be considered to have been randomized. Since the primary interest of this study is treatment in participants with standard risk acute GVHD, the primary analysis population will consist of all randomized AA1/2 participants with treatment classified per the ITT principle.

The primary analysis for the primary, secondary, and exploratory endpoints will use the primary analysis population. A secondary analysis of the primary endpoint will be

performed, classifying participants by the initial treatment actually given. Another secondary analysis will consider primary and key secondary outcomes for all randomized AA3 participants classified per the ITT principle. An analysis of safety endpoints will also be conducted using the safety analysis population as described below. Analyses of each endpoint and population used will follow the analysis plan as described below in section 4 of this SAP.

If a participant is deemed not eligible for the study after study registration or randomization occurs, he will be excluded from all analysis populations.

## **2.8.2 Safety Analysis Population**

The reporting of serious adverse events will be consistent with standard BMT CTN procedures with the addition of any anticipated SAE related to sirolimus or prednisone therapy. All reported serious adverse events potentially associated with a study drug will be carefully examined with respect to the severity and relationship to the study drug. The type and severity of adverse events will be described. Safety data will be summarized using Medical Dictionary for Regulatory Activities (MeDRA) Coding Version 20.0 or above.

The safety analysis population will be the same as the primary analysis population: all randomized AA1/2 participants categorized according to ITT.

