##### **1.1.3 Exploratory Objectives**

The exploratory objectives of the study are to assess:

- Cumulative steroid dose (prednisone-equivalent) through Day 56 post randomization.

- Use of topical (skin, GI) agents for acute GVHD therapy at baseline and during the study's duration.
- Incidence of discontinuation of immune suppression, and immune suppression discontinuation without GVHD or disease progression/recurrence by Days 56, 180, and 365 post-therapy.
- Incidence of EBV-associated lymphoproliferative disorder or EBV reactivation requiring therapy
- Incidence of corticosteroid- and sirolimus-associated complications (collected in all participants):
- Incidence of hyperglycemia (defined as a random glucose >200mg/dL or fasting glucose >126mg/dL) and use of diabetes therapy (use of insulin and/or oral medications to control and/or maintain glucose levels) at baseline, Day 28 and Day 56.
- Hip Flexor and Quadriceps Strength score via handheld dynamometer at baseline, Day 56, and 6 months post-randomization
- Two Minute Walk Test score at baseline, Day 56, and 6 months post-randomization
- 5-time Sit-to-Stand Test score at baseline, Day 56, and 6 months post-randomization
- Adult Myopathy Assessment Tool (AMAT) score at baseline, Day 56, and 6 months post-randomization
- Incidence of hyperlipidemia as measured by fasting lipid panel at baseline, Days 28, 56 and 180 post-randomization.
- Incidence of post-transplant thrombotic microangiopathy (TMA) by 6 months post-randomization.
- Proportion of participants requiring therapy for CMV-reactivation by day 56 post-randomization.
- Change in patient-reported outcomes from enrollment to Day 56, 6 months and 12 months.
- MD Anderson Symptom Inventory (MDASI) score at baseline, Day 56, 6 months, and 12 months post-randomization
- FACT-BMT score at baseline, Day 56, 6 months, and 12 months post-randomization
- MOS Short Form 36 (SF-36) score at baseline, Day 56, 6 months, and 12 months post-randomization
- PedsQL (Pediatric participants) score at baseline, Day 56, 6 months, and 12 months post-randomization
- A secondary descriptive analysis will evaluate all study outcomes in AA3 participants.

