### **1.5 Response Variables and Data Collection Time Points**

The response variables for this study include the primary, secondary, and safety endpoints. The primary endpoint is CR/PR at Day 28. Secondary endpoints include:

- CR/PR at Day 28 with steroid dose of 0.25mg/kg/day or less
- Disease response
- Treatment failure
- Chronic GVHD
- Systemic infection
- Event-free survival
- Overall survival
- Disease-free survival
- GVHD-free survival
- Non-relapse mortality
- Steroid dose
- Topical steroid therapy
- Discontinuation of immune suppression
- EBV-associated lymphoproliferative disorder
- Hyperglycemia
- Functional myopathy
- Hyperlipidemia
- Thrombotic microangiopathy
- CMV reactivation
- Patient-reported outcomes

Safety endpoints included mortality, toxicity, and adverse events. Safety monitoring will be conducted per protocol schedule as described in Section 2.4 of this SAP. Adverse events will be reported per the BMT CTN (Manual of Procedures) MOP.

Definitions for each endpoint are described in detail in the protocol and in section 4 of this SAP.

Participants are required to complete both pre-randomization and post-randomization assessments. Pre-randomization assessments must be performed prior to and as close as possible to the participant's enrollment / randomization on the trial. Post-randomization assessments occur weekly up to Day 56 and then occur at Day 90, 180,

and 365 post-randomization. Data from these evaluations are collected on calendar-driven clinical forms. Deaths, infections, hospitalizations, and adverse events are reported on event-driven clinical forms.

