#### **4.3.11 Secondary Analysis of AA3 Participants**

A secondary analysis will assess study outcomes for AA3 participants by treatment group (note that participants with missing biomarker results will be excluded). Due to the small number of AA3 participants expected, this analysis will be descriptive only as we are unlikely to have power to detect differences between the groups.

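### The SAP's safety population omits AA3 and missing-result patients who will normally have been dosed (about 30 of 150), and its ineligibility sentence allows unblinded removals from every analysis set

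*SAP*

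**What the plan says.** **Safety set.** SAP 2.8.2: "The safety analysis population will be the same as the primary analysis population: all randomized AA1/2 participants categorized according to ITT". SAP 1.5 says what the set has to serve: "Safety endpoints included mortality, toxicity, and adverse events".

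**Timing.** Protocol 2.5.1 allows at most 24 hours from randomisation to first dose. The synopsis places the Ann Arbor result at 48 to 72 hours after randomisation; Protocol 2.5.2 says within 72 hours, usually within 48. Protocol 2.5.2 lets AA3 and missing-result patients stay on the randomised drug or move to another at the physician's discretion, and requires the full assessment schedule in every patient.

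**AA3 patients.** The SAP describes their analysis in three places. SAP 1.1.3: "A secondary descriptive analysis will evaluate all study outcomes in AA3 participants". SAP 4.3.11: "A secondary analysis will assess study outcomes for AA3 participants by treatment group". SAP 2.8.1: "Another secondary analysis will consider primary and key secondary outcomes for all randomized AA3 participants classified per the ITT principle".

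**Missing-result patients.** They have a row in the baseline shell (Exhibit 1501-2) and are left out of SAP 4.3.11. The protocol is divided: the synopsis, 2.5.2 and 5.1.3 say they will be included or described in a secondary analysis, while 3.3.8 and 5.2.7 exclude them from the AA3 analysis.

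**Who counts as randomised.** SAP 2.8.1 says "Any participant who receives a treatment randomization number will be considered to have been randomized" and builds the primary set from every randomised AA1/2 patient. It ends: "If a participant is deemed not eligible for the study after study registration or randomization occurs, he will be excluded from all analysis populations".

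**The concern.** Biomarker risk can define the population in which efficacy is estimated, but it does not undo exposure to a drug. A safety set restricted by a result that arrives after the first dose leaves exposed patients out of the tables meant to describe harm. If no other part of the SAP assigns those patients' adverse events to a table, whether they are reported becomes a matter of choice at the time of analysis.

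The ineligibility sentence raises a different risk. The trial is open label, and the primary result is an estimated difference with about 60 patients per arm. The SAP does not say who rules on eligibility after randomisation, by when, on what evidence, or whether that person knows arm and outcome. A ruling made with both known can change who counts in the primary difference. Because it applies to all populations, it also takes a dosed patient out of the safety tables.

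**Working it through.** **1. Plan's own figure.** Inputs: 120 AA1/2 patients to be analysed, 20% AA3 or missing (Protocol synopsis and 5.1), 1:1 allocation. 120 / (1 − 0.20) = 150, as stated. Outside the safety set: 150 − 120 = 30, or 30 / 2 = 15 per arm.

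**2. Range.** With a true share of 20%, the 95% binomial range in 150 patients is 21 to 40. With a share of 15% to 25% (assumed), the expected count is 22.5 to 37.5. The documents disagree on what the 20% covers: AA3 plus missing in the synopsis and Protocol 5.1, AA3 alone in Protocol 5.2.2.2 and 5.2.7. If it is AA3 alone, each percentage point of missing results adds 150 × 0.01 = 1.5 patients, and the count exceeds 30. No missing-result rate is given.

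**3. Which rule governs the tables.** SAP 2.8.1 refers onward: "Analyses of each endpoint and population used will follow the analysis plan as described below in section 4 of this SAP".
- Section 4 covers mortality (4.2.7, 4.2.10), infections (4.2.5) and named complications (4.3.4 to 4.3.9). It has no general toxicity, AE or SAE analysis.
- Exhibit 1501-23 and Supplemental Exhibits 1501-4 and 1501-5 tabulate by treatment group and name no population.
- Analysis by treatment actually given is planned in 2.8.1 for the primary endpoint only.
- Sequential safety monitoring is also limited to AA1/2 patients (Protocol 5.2.2, SAP 2.5).

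So 2.8.2 is the only population rule for those three exhibits.

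**4. Precision.** Assume all 30 are dosed and split evenly, so that n per arm goes from 60 to 60 + 15 = 75. The event rates are illustrative.

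| Quantity | Formula | n = 60 | n = 75 |
|---|---|---|---|
| 95% upper bound, no events seen | 1 − 0.05^(1/n) | 4.9% | 3.9% |
| Chance of at least one event, true rate 1% | 1 − 0.99^n | 45.3% | 52.9% |
| Same, true rate 2% | 1 − 0.98^n | 70.2% | 78.0% |
| Same, true rate 3% | 1 − 0.97^n | 83.9% | 89.8% |

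These gains are upper limits, because the added patients may change therapy once the result arrives.

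**5. Ineligibility sentence.** Take a randomised AA1/2 patient later ruled ineligible. The randomisation-number rule and the definition of the primary set put that patient in; the closing sentence of the same section takes the patient out. Both cannot apply. The documents give no rate of late ineligibility, so the effect cannot be sized. Illustration only: removing 3 non-responders from an arm with 36/60 = 60.0% gives 36/57 = 63.2%.

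**The case against.** **Harm is not unobserved.** A reader might infer that adverse events in some 30 patients go unseen. The documents do not support that. All patients complete all assessments (Protocol 2.5.2 and 4.4), unexpected SAEs are reported and summarised to the DSMB (Protocol 4.6.1), and the sentence in SAP 2.8.2 on examining drug-associated SAEs has no AA1/2 limit. This objection stands: the gap is in the planned tables.

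**AA3 patients are partly covered.** Nor are all 30 without any analysis. SAP 1.1.3 and 4.3.11 are worded broadly enough to take in safety, and SAP 1.5 counts safety endpoints among the response variables. Only 2.8.1 is narrower. This also stands, although none of the three passages expressly assigns the toxicity, AE and SAE tables to AA3 patients. The group with no SAP outcome summary at all is the missing-result group, whose size is not given. The SAP did not simply drop a protocol promise to them, since the protocol contradicts itself.

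**AA1/2 is the target population.** Pooling by first drug could charge months of events to a drug taken for two or three days. That is a fair argument for separate columns, but not for leaving the patients out. Assigned and first-received drug should seldom differ, so the regrouping itself will change little.

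**ITT.** Two stronger readings fail. The AA1/2 restriction does not break ITT, because the sample is drawn before randomisation. The closing sentence of 2.8.1 does not contradict the SAP's explanation of ITT, which concerns arm classification and treatment not given and is silent on eligibility. The conflict is with the primary set and the randomisation-number rule. Protocol 5.1 gives the exclusion some support, since it sets its target as patients who are both eligible and randomised. Eligibility is also checked before assignment (Protocol 4.2), so late rulings should be few.

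**Conclusion.** Both points hold and should be fixed; neither undermines the design or the sample size.

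On safety, about 30 of 150 randomised patients (a planning figure) will normally be dosed but lie outside the set used for the toxicity, AE and SAE exhibits. For AA3 patients the remedy is mainly to settle an inconsistent scope. For missing-result patients the SAP has no outcome or safety summary. The improvement in the zero-event bound, from 4.9% to 3.9%, is the most that could be gained. It assumes that all 30 are dosed, split evenly and informative about the first drug.

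On eligibility, the closing sentence of SAP 2.8.1 conflicts with the set defined just above it. In an open-label trial without safeguards it can bias the primary difference. The 3.2-point shift in the illustration (63.2 − 60.0) is an invented one-sided case and not an estimate; for scale, the planned 90% interval extends about 15 points below the estimate at 60 per arm.

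**What to change.** - **SAP 2.8.2:** define the safety population as all randomised participants who received at least one dose of study drug, grouped by drug first received. In Exhibit 1501-23 and Supplemental Exhibits 1501-4 and 1501-5, show AA1/2, AA3 and missing-result patients in separate columns, with a note of later therapy.
- **SAP 1.1.3, 2.8.1 and 4.3.11:** use one statement of which AA3 outcomes are described, and say whether the adverse-event tables are among them. State where missing-result patients are described, and reconcile the protocol sections that disagree about them.
- **SAP 2.8.1:** delete the closing sentence. Keep every randomised AA1/2 patient in the primary analysis and every dosed patient in the safety set. Exclude ineligible patients only in a sensitivity analysis, with ineligibility resting on pre-randomisation facts and judged blind to arm and outcome.

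**Cost:** SAP wording and extra table columns, with no new data, since the full assessment schedule already applies to every patient. A few ineligible patients will remain in the primary analysis, and some events after a switch will be attributed to the first drug. The separate columns and the therapy note limit the second of these.

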## **2.9 General Analysis Guidelines**

Continuous variables will be described using the mean, standard deviation, median, and range. Categorical variables will be described using frequencies and proportions. All statistical tests will be two-sided at a 0.05 significance level unless otherwise specified.

Any changes to the planned analyses and addition of any ad-hoc analyses will be documented in the final analysis report with justification given for the changes. If it is a change to analysis of an existing endpoint, the change should be clearly stated in the exhibit. If a new endpoint or analysis is performed, it should be included as a supplemental exhibit.

## **3. Participant Characteristics and Compliance**

### **3.1 Demographics and Baseline Characteristics**

Descriptive statistics for demographics and baseline characteristics of participants and donors will be presented by treatment group. Characteristics to be examined are: age, gender, race/ethnicity, performance status, primary disease, risk status, transplant conditioning regimen characteristics, donor type, HLA matching, graft source, initial GVHD prophylaxis delivered, donor and recipient CMV status, acute GVHD organ staging and overall grade at enrollment, and topical steroid therapy use.

Data on performance status, primary disease, risk status, conditioning regimen characteristics, donor type, HLA matching, graft source, initial GVHD prophylaxis, and

donor and recipient CMV status will be retrieved from the CIBMTR database. All other variables will be collected on clinical forms.

### 3.2 Participant Compliance

A table listing significant protocol deviations/violations will be provided with treatment assignments indicated. Compliance with protocol interventions will be evaluated as appropriate. Premature withdrawals will be described for each case.

A consort diagram will be provided to illustrate study accrual, participant disposition, and follow up.

The number of participants evaluated will be described in the tables and figures for each analysis.

## 4. Analysis Plan

### 4.1 Analysis of the Primary Endpoint

The primary endpoint for this study is complete response/partial response (CR/PR) of acute GVHD to therapy at Day 28 post-randomization. No formal hypothesis test will be performed. Instead, the difference in response rates between the two arms will be estimated with a 90% confidence interval.

Acute GVHD response is categorized as complete response (CR), partial response (PR), mixed response (MR), no response (NR), and progression and is scored relative to the participant's acute GVHD status (organ staging) entered on the day of randomization. Response categories are defined as follows:

- **Complete response (CR):** A stage of 0 for the GVHD grading in all evaluable organs. For example, for a response to be scored as CR at Day 28, the participant must still be in CR on that day and have had no intervening additional therapy for an earlier progression, PR or NR.
- **Partial response (PR):** Improvement in one or more organs involved with GVHD symptoms without progression in others.
- **Mixed response (MR):** Improvement in one or more organs with either deterioration in another organ manifesting symptoms of GVHD or development of symptoms of GVHD in a new organ.
- **Progression:** Deterioration in at least one organ without any improvement in others.
- **No response (NR):** Absence of any improvement or progression

Patients receiving secondary therapy (including need to re-escalate steroid dose to  $\geq 2.5$  mg/kg/day of prednisone [or methylprednisolone equivalent of 2 mg/kg/day]) will be classified as non-responders. Patients who are assigned to the sirolimus arm who require initiation of systemic corticosteroids for the treatment of acute GVHD will be considered as non-responders for purposes of the primary endpoint assessment.

Participants that have died prior to Day 28 will be treated as nonresponders in the analysis.

The reference for response evaluation is the GVHD organ staging reported at enrollment. The response rate (CR/PR) at Day 28 will be estimated using frequencies in each treatment group. A 90% Wald confidence interval for the difference in rates of the treatment groups will be computed.

In a secondary analysis, rates of Day 28 CR/PR and their 95% confidence intervals will be estimated for each treatment group by donor type, graft source, and HLA mismatch (matched vs. mismatched). As the numbers for these subgroup analyses will be small, the intent is not to declare differences between subgroups formally, but rather to identify potential differences that may need to be considered in future trials.

## **4.2 Analysis of the Secondary Endpoints**

Since this is a phase II trial with many secondary and exploratory endpoints, no explicit control for multiplicity will be incorporated; rather a significance level of 5% will be used for all comparisons on these outcomes.

### **4.2.1 Proportion of Participants with CR/PR and Steroid Dose 0.25 mg/kg/day or Less**

This is a refined endpoint of CR/PR and the use of a prednisone equivalent steroid dose of 0.25 mg/kg/day or less. The rates of CR/PR and steroid dose 0.25 mg/kg/day or less will be estimated within each arm and compared between arms using the Z test for binomial proportions (or Barnard's Exact Unconditional Test as appropriate). Methylprednisone is considered to be 1.25 times as potent as prednisone, while prednisolone is dose-equivalent to prednisone. Note that use of prednisone below the threshold on the sirolimus arm will not be considered a failure for this endpoint. Participants that have died prior to Day 28 will be treated as nonresponders in the analysis.

### **4.2.2 Disease Response**

The rates of complete response, partial response, mixed response, no response, and progression among surviving participants at Day 14, 28, and 56 will be estimated for each treatment group and compared between groups using Pearson's chi-square test (or Fisher's Exact Test as appropriate).

### **4.2.3 Treatment Failure**

Treatment failure is a composite endpoint comprised of death, no response, progression, administration of additional therapy beyond primary therapy for GVHD [(or re-escalation of steroid dose to  $\geq 2.5$  mg/kg/day of prednisone (or methylprednisolone equivalent of 2 mg/kg/day) or initiation of corticosteroids for the treatment of acute GVHD for participants assigned to the sirolimus arm] at Days 14, 28, and 56. Proportions of treatment failures for the treatment arms will be estimated and compared at Days 14, 28

and 56 using the Z test for comparing binomial proportions (or Barnard's Exact Unconditional Test as appropriate).

#### **4.2.4 Chronic GVHD**

Chronic GVHD is defined by NIH Consensus Criteria. Cumulative incidence of chronic GVHD per this Criteria will be estimated for each treatment arm using the Aalen-Johansen estimator and compared between arms using Gray's test, treating death and relapse as competing risks. Estimates and confidence intervals will be provided at 6 and 12 months post-randomization.

#### **4.2.5 Systemic Infections**

Frequencies of infections will be tabulated by site of disease, date of onset, and severity. The time to first serious infection (Grade 2 or 3 per BMTCTN MOP) will be estimated for each treatment arm using the Aalen-Johansen estimator and compared between arms using Gray's test, treating death as the competing risk. For the definition of infection severity, see the BMT CTN Manual of Procedures.

